## VIII. CLINICAL INVESTIGATIONS

General Assessment	UK study site Responsibility	Harpoon Medical Responsibility	Screening and pre-operative evaluation	Surgery Date	Discharge	30 Days (+10-0 d)	6 Months (+/- 30 d)	12 Months (+/- 30 d)	18 Months (+/- 30 d)	24 Months (+/- 30 d)	30 Months (+/- 30 d)	36 Months (+/- 30 d)	48 Months (+/- 30 d)	60 Months (+/- 30 d)
Invitation to enroll in the TRACER study	X		X											
Screening worksheet completed	X		X											
Patient Eligibility Committee Assessment		X	X											
Patient Information Sheet Signed*	X		X											
Pre-Procedure worksheet completed	X		X											
Release of Medical Information **	X		X											
Medical History **	X		X		X	X	X	X	X	X	X	X	X	
Medications & Dosage **	X		X	X	X	X	X	X	X	X	X	X	X	
Physical Exam **	X		X	X	X	X	X	X	X	X	X	X	X	
Laboratory Assessment (blood work)	X		X											

\* An additional Patient Information Sheet will be signed by the subject(s) to reflect the additional follow-up required by this protocol amendment

\*\* - included as part of the baseline/pre-procedure worksheet

Cardiac Assessment	UK study site Responsibility	Harpoon Medical Responsibility	Screening and pre-operative evaluation	Surgery Date	Discharge	30 Days (+10-0 d)	6 Months (+/- 30 d)	12 Months (+/- 30 d)	18 Months (+/- 30 d)	24 Months (+/- 30 d)	30 Months (+/- 30 d)	36 Months (+/- 30 d)	48 Months (+/- 30 d)	60 Months (+/- 30 d)
Chest Radiograph (X-Ray)	X													
Diagnostic Left Heart Catheterisation or Clinical Standard of Care	X		X											
NYHA Heart Failure Class	X		X		X	X	X	X	X	X	X	X	X	
Electrocardiogram (ECG)	X		X		X									

Transthoracic Echocardiogram (TTE) ***	X		X		X	X	X	X	X	X	X	X	X	X
Transoesophageal Echocardiogram (TOE)	X		X	X										
SF-36 Quality of Life Assessment	X						X							
6 Minute Walk Test	X						X							
EUROscore risk assessment	X													
Pulmonary Function Test (if clinically indicated)	X													

\*\*\* TOE: may be required if the TTE images are not readable

## RETROSPECTIVE COLLECTION OF DATA

Protocol Version 00k extends the patient follow-up with visits at 48 and 60 months. The Protocol Version 00j had introduced additional follow-up visits at 18, 30 and 36 months. These protocols allow retrospective collection of data on any scheduled or unscheduled visit that the subjects participated in for the TRACER trial (if subject came back to the hospitals) before Versions 00j or 00k are approved by Ethic Committee (EC) and Competent Authority (CA).

Once Protocol Version 00k has been approved by relevant EC and CA, patients will be contacted and asked to consent to the additional visits and have their data collected. Patients who exited from the trial at 36 months as scheduled per protocol Version 00j will be contacted and requested to continue their follow-up up to 60 months as scheduled by Protocol Version 00k.

Two different versions of information letters will be sent depending on patient status (already exited or not). Each patient will have to sign this letter to approve collection of additional data.

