## II. STUDY SUMMARY

Title:	Mitral TR ans- A pical Ne o C hordal E cho-guided R epair (TRACER) Trial
Protocol Number:	HMCE -1002-00k
Study Status:	Enrollment was completed as of November 2017. Follow-ups range from 6 to 36 months. The purpose of this amendment is to extend to 5 years of follow-up post-implant.
Design:	This is a prospective, single arm, nonrandomised, multi-center EU study to demonstrate the performance and safety of the Harpoon Medical device in patients with degenerative MR.
Study Duration:	Projected enrollment of first patient: April 2016 Projected exit of final patient: November 2022
Primary Objective:	The primary objective of this study is to evaluate the safety and performance of the Harpoon Medical device.
Patient Population:	Patients with “Severe” mitral regurgitation as a result of posterior leaflet prolapse.
Sample Size:	Up to twenty (20) patients in the UK will be enrolled.
Number of Sites:	Up to eight (8) sites in up to four (4) countries. Each country will enroll up to twenty (20) patients.
Treatments:	Up to eight (8) pairs of ePTFE chordae tendineae may be placed in the posterior leaflet of the mitral valve using the Harpoon Medical Transapical Device in order to establish effective coaptation of the mitral leaflets.
Endpoints:	Performance endpoints:  Primary Performance Endpoints: To demonstrate that the Harpoon Medical device performs as designed and has the ability to successfully implant one or more ePTFE chordae tendineae on the mitral valve via a small left thoracotomy on the beating heart and reduce mitral regurgitation from “severe” to less than or equal to “moderate” at the conclusion of the procedure and at 30 days post-procedure.  Secondary Performance Endpoints: Severity of mitral regurgitation at 6 months, 12 months, 18 months, 24 months, 30 months, and 36 months follow-up shall be tracked and recorded.

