## SEVERITY AND CAUSALITY ASSESSMENT

The occurrence of Adverse Events (AE's) will be monitored during this study. All AE's will be recorded on the Adverse Event Form at onset and at each follow-up visit until resolved. To meet the objectives of this study, the following definitions will apply. (Definitions reference ISO 14155:2012-01 and MEDDEV 2.7/3, December 2010)

**Adverse Event (AE):** Any untoward medical occurrence, unintended disease or injury or any untoward clinical signs (including an abnormal laboratory finding) in patients, users or other persons whether or not related to the investigational medical device. This includes events related to the device or events related to the procedures involved (any procedure in the clinical investigation plan). For users or other persons, this definition is restricted to events related to investigational medical devices.

**Adverse Device Effect:** An adverse event related to the use of an investigational medical device, including adverse events resulting from insufficient or inadequate Instructions for Use, deployment, implantation, installation or operation, or any malfunction of the medical device or any event resulting from use error or intentional misuse of the medical device.

All AEs will be monitored from the time of the Harpoon Medical procedure through the 60 month follow-up visit. All AEs observed by the Investigator or staff during a physical or laboratory examination, interventional procedure, or mentioned by the patient either spontaneously or upon questioning will be recorded on the AE case report form. Information pertaining to all AEs will be reviewed and verified by the study Sponsor's Safety Team or its designated representative. The Investigator is responsible for assessing the severity of the AE, the causal relationship between any events and the clinical study procedure, activities or device. Additionally, the Investigator is responsible for providing appropriate treatment for the event and for adequately following the event until resolution. The following categories of adverse event severity are to be used:

- Mild: Awareness of a sign or symptom that does not interfere with the patient's usual activity or is transient, resolved without treatment and with no clinical sequela.
- Moderate: Interferes with the patient's usual activity

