Freedom from Serious Adverse Events (SAEs) during the ePTFE implantation procedure, at discharge, and at 30 days follow-up will be tabulated. The number of patients experiencing one or more AEs or SAEs at 30-days post-procedure, the percentage of patients, and the exact 95% confidence limit will be calculated. Patients who die prior to 30 days will be considered failures for this analysis.

Freedom from Serious Adverse Events (SAEs) at 6 months, 12 months, 18 months, 24 months, 30 months and 36 months follow-up shall be tabulated. The number of patients experiencing one or more AEs or SAEs at 6 months, 12 months, 18 months, 24 months, 30 months, 36 months, 48 months and 60 months follow-up, the percentage of patients, and the exact 95% confidence limit will be calculated.

These data shall be used to assess the safety and performance of the Harpoon Medical device, and are not designed to test a statistical hypothesis, and therefore a formal sample size has not been calculated. All data shall be captured on an intent-to-treat basis. Data shall be reported as descriptive statistics.

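### Patients who exited at 36 months and died or became unable to sign before re-consent have no clear route into the 48- and 60-month safety figures

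*Combined protocol and SAP*

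**What the plan says.** The Study Summary describes the state of the trial at this amendment: "Enrollment was completed as of November 2017. Follow-ups range from 6 to 36 months". The amendment's purpose is to lengthen follow-up to five years.

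The Section VIII subsection on retrospective data collection covers patients who had already left: "Patients who exited from the trial at 36 months as scheduled per protocol Version 00j will be contacted and requested to continue their follow-up". Under Version 00k this means visits until month 60. There is one letter for exited patients and another for those still in follow-up, and for both "Each patient will have to sign this letter to approve collection of additional data". It also permits "retrospective collection of data on any scheduled or unscheduled visit that the subjects participated in for the TRACER trial", if the patient came back to the hospital before Versions 00j or 00k were approved. It says nothing about patients who have died or cannot sign.

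On safety, Section VIII (Severity and Causality Assessment) states: "All AEs will be monitored from the time of the Harpoon Medical procedure through the 60 month follow-up visit". Section X plans "The number of patients experiencing one or more AEs or SAEs at 6 months, 12 months, 18 months, 24 months, 30 months, 36 months, 48" and 60 months, as a percentage with an exact 95% limit. It names no denominator for these time points. Its rule that a death counts as a failure is limited to deaths before 30 days.

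**The concern.** Entry of an exited patient into the extension depends on being alive and able to sign when the site makes contact. Death and a disabling stroke are among the outcomes the late safety table should show, and they are also what prevents a signature. If such a patient drops out without being counted, the late rate is too low for a reason unrelated to the device. A reader of the final table could not see this, because no count of patients lost in this way is planned. At stake is the extra safety information that the amendment sets out to collect on a permanent implant.

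**Working it through.** **Step 1. Is there another route into the tables?**

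- *Patient Withdrawal (Section VI)* asks for final status on all patients, within the terms of the informed consent. Whether that consent covers the time after a scheduled exit cannot be settled from the text.
- *Follow-up Procedures (Section VII)* directs the additional visits at active subjects.
- *Retrospective collection (Section VIII)* is tied to trial visits. No trial visit was scheduled for an exited patient before Version 00k.
- *Documentation of SAEs (Section VIII)* asks that serious device effects after the study period be reported to authorities. It covers device-related events only and makes no link to the 48- and 60-month table.
- *Section X* gives no rule for non-signers or for deaths after 30 days.

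None of these clearly brings a death or disabling event between exit and signing into the late tabulation.

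**Step 2. Direction.** Let N be all patients, E those with an event, and L the event patients lost before signing.

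- True rate: E/N
- Signers only: (E − L)/(N − L)
- All patients, lost counted as event-free: (E − L)/N

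The signers-only rate is below E/N when N(E − L) < E(N − L), which reduces to L(N − E) > 0. That holds whenever L > 0 and not everyone has an event. The third rate is lower still, since N > N − L. The unstated denominator therefore changes the size of the bias but not its sign.

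**Step 3. Size (illustration only).** The plan gives no expected late rate, number exited or re-consent rate, so there is no figure of its own to reproduce. Assumed: a true SAE rate of 20%, with the L lost patients all having events. N is taken as 20 (the UK ceiling), 30 (the CE-mark set) or 20 × 4 = 80 (the ceiling over four countries). Limits are exact (Clopper-Pearson) 95%: for x of n, the 2.5% quantile of Beta(x, n − x + 1) and the 97.5% quantile of Beta(x + 1, n − x).

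| N | L | All events known | Signers only | All patients, lost = event-free |
|---|---|---|---|---|
| 20 | 2 | 4/20 = 20.0% (5.7–43.7) | 2/18 = 11.1% (1.4–34.7) | 2/20 = 10.0% (1.2–31.7) |
| 30 | 0 | 6/30 = 20.0% (7.7–38.6) | 6/30 = 20.0% (7.7–38.6) | 6/30 = 20.0% (7.7–38.6) |
| 30 | 1 | 6/30 = 20.0% (7.7–38.6) | 5/29 = 17.2% (5.8–35.8) | 5/30 = 16.7% (5.6–34.7) |
| 30 | 2 | 6/30 = 20.0% (7.7–38.6) | 4/28 = 14.3% (4.0–32.7) | 4/30 = 13.3% (3.8–30.7) |
| 30 | 4 | 6/30 = 20.0% (7.7–38.6) | 2/26 = 7.7% (0.9–25.1) | 2/30 = 6.7% (0.8–22.1) |
| 80 | 2 | 16/80 = 20.0% (11.9–30.4) | 14/78 = 17.9% (10.2–28.3) | 14/80 = 17.5% (9.9–27.6) |

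**Step 4. What a bound would show.** With N = 30, 4 observed events and 2 patients of unknown status, the rate lies between 4/30 = 13.3% and (4 + 2)/30 = 20.0%. The upper end recovers the assumed true rate; the signers-only 14.3% does not.

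**The case against.** Much can be said for the plan.

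- **Few patients may be affected.** First enrolment was projected for April 2016 and enrolment closed in November 2017, about 19 months later. When the first patient reached 36 months, the last was near 36 − 19 = 17 months. Only those who had exited before signing are exposed, and eligibility excludes the sickest patients. This stands as a limit on size. It does not show that the number is zero, and the date of approval and re-contact is not given.
- **Signers are questioned.** A reader might infer that an SAE treated elsewhere between exit and re-consent is lost even for a patient who signs. The documents do not support that. Adverse events mentioned spontaneously or on questioning are recorded, device effects are asked about at each contact, and medical history is on the follow-up schedule. What is missing is only an explicit look-back to the exit date.
- **Consent may already reach further.** The final-status rule refers to the informed consent, and the schedule lists a release of medical information at screening. Nothing shows that the consent meant there is only the new letter, so existing authority to check records cannot be ruled out. Nor is it stated, and Section X does not use it.
- **A signature is the proper default.** Paragraph 32 of the Declaration of Helsinki (Appendix A) expects consent for the use of identifiable data, with exceptions through an ethics committee. This stands, and any status check should go through that route.
- **The output is descriptive.** Primary endpoints are at the procedure and 30 days, listed secondary endpoints stop at 36 months, and the CE mark was already granted. This lowers the severity without removing the bias.

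**Conclusion.** The point holds in a limited form. For patients who exited at 36 months, a death or incapacity before signing has no clear route into the 48- and 60-month safety figures, and that loss can only lower the reported rate. Under the stated assumptions, two such patients among 30 move the rate from 20.0% to 14.3% (signers only) or 13.3% (counted as event-free). With none lost there is no bias.

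A reader might go further and conclude that the late rates describe only survivors. They do not: deaths before the 36-month exit fall within the earlier follow-up, deaths after signing are captured, and patients still in follow-up receive their own letter while active. Nor can it be said that the lost patients leave both numerator and denominator, since the denominator is not stated. A more dramatic example, with three deaths in the gap giving 0/27 in place of 3/30 = 10.0%, is arithmetically possible, but nothing in the documents anchors it.

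Severity is moderate: the effect runs in one direction and would not be visible in the planned tables, but it concerns descriptive results outside the listed endpoints.

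**What to change.** 1. **Section X.** Report 48- and 60-month safety on all implanted patients. Show how many were followed, known dead before re-consent, unable to sign, refused and not reached. Add those who left before 36 months, so that the rows sum to the number implanted. Count known deaths as events, and add a bound that counts every patient of unknown status as an event.
2. **Section VIII, retrospective collection.** Subject to ethics approval and respecting refusals, establish vital status for exited patients who cannot be re-consented. At the first extension contact, ask each signer explicitly about SAEs since the exit date, wherever treated.

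The cost is a paragraph in the amendment and its ethics submission, a small record check, and a few table rows. The late rates may look somewhat less favourable. If no exited patient was lost before signing, the disposition counts will show it and the main figures will be unaffected by this problem.

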## SEVERITY AND CAUSALITY ASSESSMENT

The occurrence of Adverse Events (AE's) will be monitored during this study. All AE's will be recorded on the Adverse Event Form at onset and at each follow-up visit until resolved. To meet the objectives of this study, the following definitions will apply. (Definitions reference ISO 14155:2012-01 and MEDDEV 2.7/3, December 2010)

**Adverse Event (AE):** Any untoward medical occurrence, unintended disease or injury or any untoward clinical signs (including an abnormal laboratory finding) in patients, users or other persons whether or not related to the investigational medical device. This includes events related to the device or events related to the procedures involved (any procedure in the clinical investigation plan). For users or other persons, this definition is restricted to events related to investigational medical devices.

**Adverse Device Effect:** An adverse event related to the use of an investigational medical device, including adverse events resulting from insufficient or inadequate Instructions for Use, deployment, implantation, installation or operation, or any malfunction of the medical device or any event resulting from use error or intentional misuse of the medical device.

All AEs will be monitored from the time of the Harpoon Medical procedure through the 60 month follow-up visit. All AEs observed by the Investigator or staff during a physical or laboratory examination, interventional procedure, or mentioned by the patient either spontaneously or upon questioning will be recorded on the AE case report form. Information pertaining to all AEs will be reviewed and verified by the study Sponsor's Safety Team or its designated representative. The Investigator is responsible for assessing the severity of the AE, the causal relationship between any events and the clinical study procedure, activities or device. Additionally, the Investigator is responsible for providing appropriate treatment for the event and for adequately following the event until resolution. The following categories of adverse event severity are to be used:

- Mild: Awareness of a sign or symptom that does not interfere with the patient's usual activity or is transient, resolved without treatment and with no clinical sequela.
- Moderate: Interferes with the patient's usual activity
- Serious: Any fatal or immediately life-threatening clinical experience that requires a patient to be hospitalised, or hospitalisation is unduly prolonged because of potential disability or danger to life or because an intervention has been necessitated. This includes any permanently disabling event.

**Device deficiency:** Inadequacy of a medical device related to its identity, quality, durability, reliability, safety or performance, such as a malfunction, misuse or use error and inadequate labeling.

**Investigational medical device:** A medical device being assessed for safety or performance in a clinical investigation. This includes medical devices already on the market that are being evaluated for new intended uses, new populations, new materials or design changes.

**Serious Adverse Device Effect (SADE):** An adverse device effect that has resulted in any of the consequences characteristic of a Serious Adverse Event.

**Serious Adverse Event (SAE):** A serious adverse event is any problem encountered in a licensable clinical trial that has led to death or to a serious deterioration in the health of a patient that either resulted in: a life-threatening illness or injury; or a permanent impairment of a body structure or a body function; or in-patient hospitalisation or prolongation; or medical or surgical intervention to prevent life-threatening illness or injury or permanent impairment to a body structure or a body function. This includes device deficiencies that might have led to a serious adverse event if suitable action had not been taken or if intervention had not been made or if circumstances had been less fortunate.

Note: Planned hospitalisation for a pre-existing condition, or a procedure un-related to the mitral valve treatment or a procedure required by this study, that is without serious deterioration in health, is not considered a serious adverse event.

SAEs must be reported via eCRF (electronic case report form) immediately but no later than 3 calendar days upon site awareness.

All SAEs and device deficiencies (reported by Investigators or identified by Safety) will be adjudicated by an independent Clinical Endpoint Committee (CEC) through the 36 month follow-up, based on relevant source documents provided from the investigational sites.

The CEC will verify SAE criteria and code. For all confirmed SAEs, CEC will also conduct a causality assessment in regards to the investigational Harpoon device and the index procedure. All adjudication activities are managed by Sponsor's Safety team according to the CEC Charter.

**Unanticipated Serious Adverse Device Effect (USADE):** Serious adverse device effect which, by its nature, incidence, severity or outcome has not been identified in the current version of the risk analysis report.

UADEs must be reported to MedPass Limited by telephone and/or email within 24 hours upon site awareness.

## REPORTING ADVERSE EVENTS, DEVICE MALFUNCTIONS AND FAILURES

All SAEs and Investigational Medical Device deficiencies that might have led to a SAE if suitable action had not been taken or if intervention had not been made or if circumstances had been less fortunate or if any new findings/updates in relation to already reported event have been made. These events shall be recorded on the Adverse Event CRF by the Investigator (or his/her designee) immediately but no later than 3 calendar days upon site awareness. The report should include: identification of the event, country, study center, patient ID code, date of procedure/first use, date of event onset, description of the event, action/treatment/patient outcome, assessment of relationship to the procedure (yes, no, possibly), assessment of relationship to the investigational device (yes, no, possibly), unanticipated SADE (yes/no), event status (resolved, resolved with sequela, ongoing, death), and the date of the event resolution.

In the case of serious adverse events (SAE), procedure and/or device failures and malfunctions, medical record documentation (e.g., procedure notes, operative notes, discharge summary, relevant progress notes, imaging or lab studies) must be provided to Harpoon Medical or its designee, if requested. If appropriate, the event shall subsequently be reported to the relevant Ethics Committee, and the Sponsor shall inform the Competent Authority within the appropriate timelines.

